8.1.4. ANOVA

Cardiovascular-related days hospitalized and all-cause days hospitalized will be analyzed using an analysis of variance (ANOVA) with treatment, TTR genotype (variant and wild-type), NYHA Baseline classification (NYHA Classes I and II combined and NYHA Class III), treatment-by-TTR genotype interaction, and treatment-by-NYHA Baseline classification interaction terms as factors.

8.1.5. Poisson Regression for Frequencies

Frequency of cardiovascular-related hospitalization and frequency of all-cause hospitalization will be analyzed using Poisson regression analysis with *treatment, TTR genotype (variant and wild-type), NYHA Baseline classification (NYHA Classes I and II combined and NYHA Class III), treatment-by-TTR genotype interaction, and treatment-by-NYHA Baseline classification interaction terms as factors adjusted for treatment duration.*

For the subgroup analyses by NYHA classification (NYHA Classes I and II combined and NYHA Class III), the Poisson regression analysis will have treatment, TTR genotype (variant and wild-type), and treatment-by-TTR genotype interaction terms as factors adjusted for treatment duration.

For the subgroup analyses by TTR genotype, the Poisson regression analysis will have treatment, NYHA baseline classification, and treatment-by- NYHA baseline classification (NYHA Classes I and II combined and NYHA Class III) as factors adjusted for treatment duration.

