The primary analysis uses a hierarchical combination applying the method of Finkelstein-Schoenfeld (Finkelstein 1999)¹⁶ to all-cause mortality and frequency of cardiovascular-related hospitalizations, which is defined as the number of times a subject is hospitalized (ie, admitted to a hospital) for cardiovascular-related morbidity.

Secondary Endpoints:

Analysis of the following key secondary endpoints will follow an alpha conserving strategy:

1. Change from Baseline to Month 30 on the distance walked during the 6-Minute Walk Test (6MWT) ([Appendix 4](#)).
2. Change from Baseline to Month 30 on the Kansas City Cardiomyopathy Questionnaire Overall Summary score (KCCQ-OS) ([Appendix 1.1](#)).

The following additional secondary endpoints will be analyzed without an alpha conserving strategy for multiple comparisons:

1. Cardiovascular-related mortality,
2. Frequency of cardiovascular-related hospitalization,
3. All-cause mortality,
4. TTR Stabilization at Month 1.

Study Design:

This is an international, multicenter, double-blind, placebo-controlled, randomized, 3-arm study with a 30-month treatment phase wherein subjects with transthyretin cardiomyopathy, due to either variant or wild-type TTR, will receive either 20 mg (n = 80) or 80 mg (n = 160) tafamidis or matching placebo (n = 160) once daily, in addition to standard of care. The

study includes a provision for sites to implement a blinded dose reduction to 40 mg once daily for subjects who experience adverse events that may be associated with the tolerability of treatment with tafamidis.

Selection of Subjects:

Subjects that will be included into the protocol must meet specific inclusion criteria that include but is not limited to the following:

1. A medical history of Heart Failure (HF) with at least 1 prior hospitalization for HF or clinical evidence of HF (without hospitalization) manifested by signs or symptoms of volume overload or elevated intracardiac pressures (eg, elevated jugular venous pressure, shortness of breath or signs of pulmonary congestion on x-ray or auscultation, peripheral edema) that required/requires treatment with a diuretic for improvement.
2. Evidence of cardiac amyloid by echocardiography with an end-diastolic interventricular septal wall thickness > 12 mm.
3. Presence of amyloid deposits in biopsy tissue and TTR precursor protein identification by mass spectrometry, immunohistochemistry or scintigraphy.
4. An NT-proBNP concentration \geq 600 pg/mL.

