9.3. Analysis of Secondary Endpoints

As a secondary analysis, the components of the primary endpoint (ie, all-cause mortality and frequency of cardiovascular-related hospitalizations) will be analyzed separately. All-cause mortality will be analyzed using SAS Proc Lifetest; p-values will be from the log-rank test. Kaplan-Meier survival curves for each treatment group along with median survival times (if applicable) will be presented.

All-cause mortality will also be analyzed using Cox proportional hazards model with treatment, TTR genotype (variant and wild-type), and NYHA Baseline classification (NYHA Classes I and II combined and NYHA Class III) as factors. Frequency of cardiovascular-related hospitalizations will be analyzed using a Poisson regression analysis with treatment, TTR genotype (variant and wild-type), NYHA Baseline classification (NYHA Classes I and II combined and NYHA Class III), treatment-by-TTR genotype interaction, and treatment-by- NYHA Baseline classification interaction terms as factors adjusted for treatment duration.

Cardiovascular-related mortality will also be analyzed using the Kaplan-Meier and Cox proportional methods described above.

All the analyses on the secondary endpoints described above will additionally be presented by TTR genotype (variant versus wild-type), NYHA Baseline classification, as well as dose (randomized dose group), and will be considered exploratory.

The proportion of subjects who achieved TTR stabilization in each treatment group at Month 1 will be compared using a Cochran-Mantel-Haenszel (CMH) test for proportions stratified by TTR genotype and Baseline severity (NYHA Classes I and II combined and NYHA Class III). The analysis will be performed separately by TTR genotypes (variant and wild-type) using a CMH test for proportions stratified by Baseline severity (NYHA Classes I and II

combined and NYHA Class III). The analysis will also be performed separately by Baseline severity (NYHA Classes I and II combined and NYHA Class III) using a CMH test for proportions stratified by TTR genotypes (variant and wild-type).

Analyses of TTR stabilization at Month 1 by dose (low vs. placebo and high vs. placebo) will be compared using a Cochran-Mantel-Haenszel (CMH) test for proportions stratified by TTR genotype and Baseline severity (NYHA Classes I and II combined and NYHA Class III).

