The term “censored” refers to a subject who discontinues from the trial for reasons other than death. For such subjects, there will be additional follow-up to obtain vital status (and transplant status / cardiac mechanical assist device status) at Month 30 and that information will be used in the analysis. In the case where one subject is censored before a second subject has died, and where the vital status of the first patient at Month 30 is missing, then the frequency of cardiovascular-related hospitalizations at the shorter of their follow-up times (the shorter of the 2 subjects’ study participation) will be used in assigning a +1 or -1. In the simpler case where one subject drops out but both are known to be alive at Month 30, the frequency of cardiovascular-related hospitalizations, at the shorter of their follow-up times (the shorter of the 2 subjects study participation), will be used in assigning a +1 or -1. Comparisons of cardiovascular related hospitalization frequency for subjects who completed all 30 months study duration will be based on the earlier of the two actual study durations (days).

Subjects, who discontinue for transplantation (ie, heart transplantation and combined heart and liver transplantation) or for implantation of a cardiac mechanical assist device, will be handled in the primary analysis in the same manner as death. More specifically, the time of the transplant or cardiac mechanical assist device implant will be used in the subject-to-subject comparison in the same manner as if the subject had died at that time (regardless of any additional vital status follow-up information). Data from subjects who drop out for a liver-only transplantation will be handled in the same manner as the data from all other censored subjects.

The proposed test is a score test based on the sum of the scores for the treated group. A value of $D_i = 1$ for subjects in tafamidis and $D_i = 0$ for subjects in the placebo group. Using the u_{ij} for every pair of subjects defined above, we assign a score to each subject.

The subjects are divided into 4 strata $k = 1; 2; 3, 4$. If A_k is the set of indices of the n_k subjects in the k^{th} strata and that U_i is calculated within strata (for $i \in A_k; U_i = \sum_{j \in A_k} u_{ij}$), then the test statistic is based on

$$T = \sum_k \sum_{i \in A_k} D_i U_i$$

Let m_k be the total number of subjects in the k_{th} stratum who are in the tafamidis group. Then in k_{th} strata

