Appendix 1.3. Sample SAS Code for Analyses Described in Sections 8.1.2 – 8.2.6

Sample SAS code to fit the mixed model repeated measures specified in [Section 8.1.3](#) is given below. The response variable Y is the change from baseline at the study visits.

```
PROC MIXED DATA=xxx METHOD=REML EMPIRICAL;  
CLASS pid center trt visit genotype;  
MODEL y= ybase trt visit genotype trt *visit;  
RANDOM int/SUBJECT=center;  
  
REPEATED visit /SUBJECT= pid (center) r type=UN;  
  
RUN;
```

Sample SAS code for the survival analysis specified in [Section 8.1.2](#) is given below.

```
PROC LIFETEST DATA=xxx PLOTS=(s) graphics;  
TIME dur *status(0);  
STRATA trt;  
RUN;  
  
PROC PHREG DATA=xxx;  
MODEL dur*status(0)=trt genotype NYHAbase/ ties=EXACT;  
RUN
```

Sample SAS code for the ANOVA specified in [Section 8.1.4](#) is given below.

```
PROC GLM DATA=xxx;  
CLASS trt genotype NYHAbase;  
MODEL y= trt genotype NYHAbase trt*genotype trt*NYHAbase;  
RUN;
```

Sample SAS code for the Poisson regression specified in [Section 8.1.5](#) is given below.

```
PROC DATA=xxx;  
ln_styyr=log(styyr);* log transformation to normalize duration of participation ;  
RUN;  
  
PROC GENMOD DATA=xxx;  
CLASS trt genotype NYHAbase;  
MODEL y= trt genotype NYHAbase trt*genotype  
trt*NYHAbase/ type 3 dist=poisson link=log offset=ln_styyr;  
RUN;
```

Sample SAS code for the CMH test specified in [Section 8.1.6](#) is given below. In the code below, the variable NYHA_GENOTYPE is obtained from combining NYHA baseline classification and TTR genotype into one variable (with 4 levels).

```
PROC FREQ DATA=xx;
TABLES NYHA_GENOTYPE*TRT*STABILIZED / CMH
RUN;
```

Sample SAS code for the pattern mixture analysis specified in [Section 8.1.5](#) is given below.

```
PROC MIXED DATA=xxx empirical;
CLASS pid visit center trt pattern genotype;
MODEL y= ybase visit trt genotype pattern visit*trt
trt*pattern / solution;
random int/subject=center;
repeated visit /subject= pid (center) r type=UN;
ESTIMATE 'Tafamidis vs placebo Month 30'
trt 1 -1 visit*trt 0 0 0 0 0 0 0 1 -1
trt*pattern 0.5 0.5 -0.5 -0.5 /cl e; * Placebo adjusted LSMEANS of Tafamidis
averaged over the pattern (equal weight=0.5);
run;
```

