Appendix 1.4. Details of Multiple Imputation Method to be Used in Sensitivity Analysis

For purposes of the missing data sensitivity analyses, the study duration of 30 months will be partitioned into 3 intervals of 10 months each. These will be referred to as period 1, period 2, and period 3, representing months 1-10, 10-20, and 20-30 respectively. Imputation models will be estimated and applied separately for each treatment group. Hospitalizations are not imputed for subjects after their death. The imputation procedure consists of two distinct phases: 1) models for cardiovascular-related hospitalization rates are estimated for each time interval, and 2) these models are then used to impute the number of cardiovascular hospitalizations following censoring (dropout) amongst subjects who dropout in an interval. Dropouts are the only source of missing hospitalization data, so there will be a monotone missing data pattern. The two-stage multiple imputation process developed here follows the procedure for monotone missing data in [Rubin \(1987\)](#).

Within each short time interval (10 months), a Poisson regression model with a constant rate will be assumed for hospitalization counts. No imputation is required for a patient who dies during the interval. Because the model applies only to subjects who survive the interval, and subjects who die during the interval are likely to have differing hospitalization rates, subjects who die in an interval will be excluded from the imputation model estimation. All other subjects still in the study at the beginning of the interval are included in the model estimation. The reduced exposure of dropouts during the intervals is represented by an exposure multiplier (between 0-10) of the monthly hospitalization rate ([McCullagh and Nelder, 1989](#)). The monthly hospitalization rate during the first period is a function of the baseline covariates NHYA baseline classification and TTR genotype. The monthly hospitalization rate during the second period is a function of the baseline covariates and the hospitalization counts during the first period. The monthly hospitalization rate during the third period is a function of the baseline covariates, and the hospitalization counts during the first and second periods.

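### The Poisson model for hospitalisation frequency makes no allowance for over-dispersion, so its standard error is too small if rates differ between subjects

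*SAP*

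**What the plan says.** Protocol 9.3 specifies the model for the secondary endpoint: "Frequency of cardiovascular-related hospitalizations will be analyzed using a Poisson regression analysis with treatment", followed by genotype, NYHA class (I-II against III), two treatment interactions and an adjustment for treatment duration. SAP 8.1.5 repeats it and applies it to the exploratory all-cause count as well: "Frequency of cardiovascular-related hospitalization and frequency of all-cause hospitalization will be analyzed using Poisson regression analysis with" the same factors. The PROC GENMOD call in SAP Appendix 1.3 ends with "trt*NYHAbase/ type 3 dist=poisson link=log offset=ln_styyr". No scale parameter, robust variance, negative-binomial option, dispersion check or fallback model appears in any of these places.

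Three other places bear on the point.

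- **Robust variance elsewhere.** Appendix 1.3 begins the mixed-model code with "PROC MIXED DATA=xxx METHOD=REML EMPIRICAL", and the pattern-mixture code also uses the empirical option.
- **Rates may differ.** SAP Appendix 1.4 excludes deaths from its imputation models because "subjects who die during the interval are likely to have differing hospitalization rates". It also specifies: "The monthly hospitalization rate during the second period is a function of the baseline covariates and the hospitalization counts during the first period".
- **Status of the endpoint.** The protocol summary introduces the list that contains this endpoint with "The following additional secondary endpoints will be analyzed without an alpha conserving strategy for multiple comparisons".

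**The concern.** A Poisson model fixes the variance of a subject's count at its mean. Genotype and two-level NYHA class can absorb differences between strata, but not differences between subjects within a stratum. If subject rates vary with relative variance k, the count has variance μ + kμ². The model-based standard error is then too small by a factor of about √(1 + kμ).

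This endpoint is where a reader will look to see whether hospitalisation contributes to the primary result. The by-dose, by-genotype and by-NYHA analyses use the same Poisson method, so a spurious dose or subgroup signal is also possible.

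**Working it through.** **1. The plan's own figures.** No size or power is stated for the Poisson analysis. The only figures that use the hospitalisation counts are the powers of the primary test in protocol 9.1: 96%, 80% and 90%. I simulated the SAP 8.1.1 test with the protocol 9.1 inputs: mortality 25% against 12.5% or 17.5%, 2.5 against 1.5 hospitalisations, N = 300 or 400. I assumed four equal strata and exponential death times.

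| Count distribution | 50% reduction, N=300 | 30% reduction, N=300 | 30% reduction, N=400 |
|---|---|---|---|
| Stated | 96 | 80 | 90 |
| Poisson | 100 | 99.7 | 100 |
| Gamma-Poisson, k = 1.1 | 96.0 | 81.9 | 91.5 |
| Gamma-Poisson, k = 1.2 | 95.6 | 80.6 | 90.0 |

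Poisson counts also failed to reproduce the table unstratified (100 / 99.7 / 99.9), with 20% dropout (100 / 99 / 100) and with 40% dropout (100 / 96 / 100). The documents do not state the simulated distribution, so k of about 1.2 is a back-fit. It serves below only as the upper end of a range.

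**2. Means to use.** The midpoint of the planned 2.5 and 1.5 is 2.0. Protocol 1.2.1 gives 12-month proportions with at least one cardiovascular hospitalisation of 10/29 (TRACS) and 9/35 (Fx1B-201). Read as Poisson over 30 months, these give −ln(1 − 10/29) × 2.5 = 1.06 and −ln(1 − 9/35) × 2.5 = 0.74, with midpoint 0.9.

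**3. Size of the nominal 5% test.** The approximation is 2(1 − Φ(1.96/√(1 + kμ))). At μ = 2 and k = 0.5 this is 2(1 − Φ(1.96/√2)) = 16.6%. I then simulated the full SAP model: both interactions, effect-coded, 160 against 240, 10,000 runs per setting. Assumptions were 20% mortality by month 30, NYHA III in 30%, variant genotype in 30% or 50%, gamma frailty and no covariate effects. Paired entries are for 30% / 50% variant.

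| k | Mean 2.0, SAP model (%) | Mean 2.0, robust (%) | Mean 0.9, SAP model (%) | Mean 0.9, robust (%) |
|---|---|---|---|---|
| 0 | 5.1 / 5.1 | 5.6 / 5.4 | 4.7 / 5.0 | 5.3 / 5.3 |
| 0.1 | 6.9 / 7.0 | 5.5 / 5.3 | 5.6 / 6.3 | 5.1 / 5.9 |
| 0.25 | 11.3 / 11.1 | 6.0 / 5.7 | 7.5 / 7.4 | 5.8 / 5.1 |
| 0.5 | 15.9 / 15.7 | 5.8 / 5.5 | 10.0 / 9.9 | 5.7 / 5.5 |
| 1.2 | 28.3 / 28.2 | 6.4 / 6.3 | 16.0 / 16.6 | 6.1 / 5.7 |

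The likelihood-ratio version is within 0.3 points of the Wald version. At mean 2.0 (30% variant) the model-based standard error is 0.092, against a true standard deviation of 0.129 at k = 0.5 (ratio 1.4) and 0.169 at k = 1.2 (ratio 1.8).

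**4. Death-linked rates only.** If the sole heterogeneity is a higher rate in subjects who die, the size is 5.0-5.7% at 1.5 times the survivors' rate, 5.2-6.6% at 2 times and 6.8-9.8% at 3 times.

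**5. At the design effect.** The log rate ratio is ln(2.5/1.5) = 0.51 in absolute value. At k = 1.2 the true standard deviation is 0.167 / 0.156, so z stays at about 3. Coverage of a model-based 95% interval is 84% at k = 0.5 and 72% at k = 1.2; with the robust variance it is about 94% in both cases.

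**6. Negative binomial with the SAP terms** (4,000 runs, 30% variant). At mean 2.0 the size is 4.5%, 5.2% and 6.2% at k = 0, 0.5 and 1.2. At mean 0.9 it is 4.8% and 5.7% at k = 0 and 0.5.

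**The case against.** The main objection is that the premise is not in the documents. They state no dispersion, and every figure above 5% follows from a chosen k. The Appendix 1.4 remarks concern an imputation model and give neither direction nor size, and the death-linked mechanism alone inflates little up to a doubling. The power table could reflect some other unstated feature of the simulation. The planning rates imply 12-month Poisson proportions of 1 − e^(−1.0) = 63% and 1 − e^(−0.6) = 45%, against 34.5% and 25.7% in the small, unmatched earlier studies. Lower true rates would explain that gap as well as over-dispersion would. All of this stands: over-dispersion is plausible but not shown.

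Other points also stand in part. The endpoint gates nothing. SAP 8.1.5 names no confidence interval, so the coverage figures apply to any model-based interval that is reported. The empirical option in the mixed models accompanies repeated visits, so its absence here does not prove an oversight. A Pearson-scaled variance performs about as well as the robust one.

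The robust test is itself somewhat liberal in small groups. For 20 mg against placebo (80 against 160) its size is 6.3%, 6.7% and 7.2% at k = 0, 0.5 and 1.2, against 5.2%, 16.0% and 27.8% for the SAP model. In an assumed subgroup of 48 against 72 it is 5.9%, 7.6% and 8.5%, against 4.5%, 16.7% and 28.4%.

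None of this supplies the missing variance term. Under over-dispersion the robust version is better in every setting examined.

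**Conclusion.** The concern holds as a conditional one. The specified analysis has a valid standard error only if rates are homogeneous within genotype and NYHA strata, and the plan contains no check or fallback if they are not. Over the assumed range of k from 0.1 to 1.2, true size runs from about 7% to 28% at mean 2.0, and from about 6% to 17% at mean 0.9. These figures rest on gamma frailty and on the assumed mortality and covariate proportions.

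The weight is minor to moderate. The primary analysis is unaffected: SAP 8.1.1 says "The proposed test is a score test based on the sum of the scores for the treated group", and its variance is computed from the observed scores. An effect as large as planned would still be detected. The risk is false significance, or an over-narrow interval, when the true effect on hospitalisation is small. It is worth correcting because the correction is so cheap.

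**What to change.** Before unblinding, keep the SAP 8.1.5 Poisson model with all its terms and the log follow-up offset. Add one sentence to 8.1.5 saying that the Wald p-value and the confidence interval use a robust (sandwich) variance by subject, for both the cardiovascular-related and the all-cause count. Make the matching change to the PROC GENMOD code in Appendix 1.3: a REPEATED statement with the subject as cluster. Name negative binomial regression with the same terms and offset as a sensitivity analysis, and report the estimated dispersion.

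If the counts are Poisson, the standard error is 0.090 instead of 0.091. If they are over-dispersed, it widens to its true value: about 1.4 times at k = 0.5 and 1.8 times at k = 1.2 (mean 2.0), or 1.2 and 1.4 times (mean 0.9). At the design effect with k = 1.2, power is 87-91% with effect coding, against 97-98% with the too-small standard error. With centred covariates it is about 95%, so the SAP should also state how the treatment effect is averaged over strata when the interactions are in the model. By-dose and subgroup results should carry a note that the robust test is slightly liberal at those sizes.

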9.1. Sample Size Determination

The primary comparison of interest is the pooled tafamidis 20 mg and 80 mg treatment groups vs. placebo. The target sample size is 400 subjects.

A sample size of 400 subjects is based on findings from study Fx1B-201 (a 12-month, open-label study of tafamidis in TTR-CM subjects), TRACS (an observational study with no treatment intervention other than standard of care in TTR-CM subjects), an understanding of current clinical outcomes in this population, and the uncertainty of the assumptions derived from these limited data.

Given that no closed-form sample size estimation solution is available for the primary analysis method, sample size estimation was performed based on simulations.

Sample size assumptions include:

1. All-cause mortality rate of 12.5% for the tafamidis group and 25.0% for the placebo group (ie, a 50% reduction in mortality with treatment).
2. 1.5 cardiovascular-related hospitalizations for the tafamidis group and 2.5 cardiovascular-related hospitalizations for the placebo group.
3. Treatment duration of 30 months.
4. Significance level (alpha) of 0.05 (two-sided test).

With these assumptions, 300 subjects (n=120 for placebo, n=60 for 20 mg, n=120 for 80 mg) yields a power of over 90% for the primary comparison. A more conservative assumption of 30% reduction in mortality (17.5 % for tafamidis and 25% for placebo) yields a power of approximately 80%. With an assumption of 30% reduction in mortality and increasing the number of subjects to 400 subjects (n=160 for placebo, n=80 for 20 mg, and n=160 for 80 mg) yields a power of approximately 90%.

Summary of operating characteristics:

| Assumptions | Sample Size | Power |
|--|--------------------|--------------|
| 50% mortality reduction, hosp frequency 2.5 (pbo), 1.5 (taf) | N=300 | 96% |
| 30% mortality reduction, hosp frequency 2.5 (pbo), 1.5 (taf) | N=300 | 80% |
| 30% mortality reduction, hosp frequency 2.5 (pbo), 1.5 (taf) | N=400 | 90% |

pbo=placebo, taf=tafamidis

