8.2.3. Secondary Analyses

The "cardiovascular -related mortality" in all analyses, unless otherwise specified, will combine deaths adjudicated as cardiovascular-related with deaths adjudicated as indeterminate.

The cardiovascular-related mortality and all-cause mortality will be analyzed using survival analysis methods detailed in [Section 8.1.2](#).

Frequency of cardiovascular-related hospitalizations will be analyzed using the Poisson regression analyses detailed in [Section 8.1.5](#).

All the analyses on the secondary endpoints described above will additionally be presented by TTR genotype (variant and wild-type), NYHA baseline classification as well as dose (randomized dose group) and will be considered exploratory.

The proportion of subjects who achieved TTR stabilization in each treatment group at Month 1 will be compared using a Cochran-Mantel-Haenszel test detailed in [Section 8.1.6](#).

A similar test of proportion will be done on TTR stabilization at all other time points and considered exploratory. No subgroup analyses will be done at these other time points.

Except for the analyses by dose group, all analyses of the secondary endpoints, including the proposed exploratory analyses of these endpoints will compare the pooled tafamidis group with the placebo group.

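### The overall Poisson and ANOVA models carry treatment-by-subgroup interactions and name no overall contrast, so the requested Type 3 test is an equal-weight subgroup average that loses precision when the subgroups are unequal

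*SAP*

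**What the plan says.** The overall Poisson model in SAP 8.1.5 has treatment, TTR genotype and NYHA group, plus "treatment-by-TTR genotype interaction, and treatment-by-NYHA Baseline classification interaction terms as factors adjusted for treatment duration". It serves cardiovascular-related hospitalization frequency (secondary) and all-cause hospitalization frequency (exploratory). Protocol 9.3 and 9.4 specify the same terms.

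The overall ANOVA for cardiovascular-related and all-cause days hospitalized (exploratory) also has "treatment-by-TTR genotype interaction, and treatment-by-NYHA Baseline classification interaction terms as factors" (SAP 8.1.4; Protocol 9.4).

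In SAP Appendix 1.3 both procedures use "MODEL y= trt genotype NYHAbase trt*genotype trt*NYHAbase". The Poisson call adds "type 3 dist=poisson link=log offset=ln_styyr". The PROC GLM call names no type of sum of squares. Neither call has an LSMEANS or ESTIMATE statement or any weights.

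SAP 8.2.3 says that, apart from the by-dose analyses, the secondary analyses "will compare the pooled tafamidis group with the placebo group". It does not say which quantity from the interaction model is that comparison.

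On status, the Protocol Summary states: "The following additional secondary endpoints will be analyzed without an alpha conserving strategy for multiple comparisons". Cardiovascular-related hospitalization frequency is in that list.

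**The concern.** Once treatment interacts with genotype and NYHA group, the model has no single treatment effect. An overall result exists only after weights for the subgroups are chosen. The text chooses none. The Type 3 option in the Poisson code chooses equal weights, and PROC GLM's Type III test would do the same. A small NYHA III group would then count as much as a large NYHA I/II group.

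Two things are at stake. The first is precision: the smaller groups have the noisier estimates, and equal weighting gives them more influence than their information supports. The second is what is estimated: if effects differ between subgroups, the answer is not the average over the enrolled population.

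The plan's other models are built differently. The Cox model (SAP 8.1.2) and the base MMRM (SAP 8.1.3) have no treatment-by-subgroup interactions; the MMRM adds them only for the subgroup analyses. SAP 8.1.5 already defines separate subgroup Poisson models, so the overall model does not need interactions to deliver subgroup results.

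**Working it through.** The plan gives no power or precision figure for these models. The 96%, 80% and 90% in Protocol 9.1 belong to the primary Finkelstein-Schoenfeld test, so there is no figure to reproduce here.

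**Inputs from the documents**
- Allocation: 160 placebo, 80 + 160 = 240 pooled tafamidis (Protocol 3; SAP 2.1).
- Planning hospitalization frequencies: 2.5 and 1.5, ratio 0.60 (Protocol 9.1).
- Genotype: at least 30% in each group, with comparable numbers intended (Protocol 3; SAP 2.1). The variant share p is therefore taken as 30-50%.

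**Assumptions**
- NYHA III share q: not given for this trial. Protocol 1.2.1 reports class III or higher in 24.1% of TRACS and 5.7% of Fx1B-201. I use 24.1-30%.
- Genotype and NYHA group independent, same mix in both arms, common treatment ratio.
- Rate ratios between subgroups: none, or 1.3 (variant) and 1.5 (NYHA III), or 2 (NYHA III alone).

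**Variance under main effects.** Expected events are 160 × 2.5 = 400 and 240 × 1.5 = 360. The variance of the log rate ratio is 1/400 + 1/360 = 0.00528 (SE 0.0726).

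**Variance ratio of the equal-weight contrast**

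VR = 1 + (0.5 − p)²/[p(1 − p)] + (0.5 − q)²/[q(1 − q)]

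With equal rates (also the ANOVA case with constant variance), p and q are the subgroup shares:
- p = 0.30: 0.04/0.21 = 0.190. p = 0.50: 0.
- q = 0.30: 0.190. q = 0.241: 0.0671/0.1829 = 0.367. q = 0.50: 0.

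| Variant / NYHA III | VR | Effective N of 400 |
|---|---|---|
| 50% / 50% | 1.00 | 400 |
| 50% / 30% | 1.19 | 336 |
| 50% / 24.1% | 1.37 | 293 |
| 30% / 30% | 1.38 | 290 |
| 30% / 24.1% | 1.56 | 257 |

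**Poisson with prognostic subgroups.** Information follows events, so p and q are replaced by event shares p' = 1.3p/(1.3p + 1 − p) and q' = 1.5q/(1.5q + 1 − q).
- 50% / 30%: p' = 0.565, q' = 0.391; VR = 1 + 0.017 + 0.050 = 1.07.
- 30% / 24.1%: p' = 0.358, q' = 0.323; VR = 1 + 0.088 + 0.144 = 1.23.
- 50% / 30% with class III at twice the rate and no genotype effect: q' = 0.6/1.3 = 0.462; VR = 1.006, about 1.01.

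The information matrix over the eight treatment-by-genotype-by-NYHA cells gives the same values.

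**Power** (normal approximation, two-sided 0.05, N = 400, equal rates). At the planning ratio of 0.60 it stays about 100% at 30/30 and 30/24.1. At an assumed ratio of 0.80, the 91% of the main-effects model becomes 86% (50/30), 80% (30/30) or 75% (30/24.1). These figures assume counts with no overdispersion.

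**Size.** Simulation with a true ratio of 1, at 30/30, gives 4.5% rejection with the interactions and 4.8% without.

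**If effects differ.** Assume ratios of 0.70 in NYHA I/II and 1.20 in NYHA III, with 30% class III and equal placebo rates. The equal-weight estimate is √(0.70 × 1.20) = 0.92. The ratio of mean rates over the enrolled mix is 0.7 × 0.70 + 0.3 × 1.20 = 0.85, which the main-effects model also gives in simulation.

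**The case against.** The strongest reply is that equal weighting comes from the Type 3 contrast and not from the interactions. A contrast from the same model weighted by observed subgroup shares has a variance ratio of 1.00 at equal rates, and the text of SAP 8.1.4 and 8.1.5 does not commit to Type 3. That stands for the mechanism. But the only instruction the plan gives for the Poisson model is Type 3, and it offers no other contrast.

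The size is also uncertain. The NYHA III share is assumed, genotype alone adds at most 0.19 because of the 30% floor, and equal rates are unlikely for the Poisson counts when SAP 6.4 uses NYHA group as the marker of baseline severity. That stands, and is why the result is a range that reaches almost 1. It also rules out stating the top of the range, 1 − 1/1.56 = 36% of information, as the expected Poisson loss.

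A reader might infer that the reported result will be the printed treatment coefficient, hence the effect in one reference subgroup. The documents do not support this. Appendix 1.3 is sample code. Its MMRM call also lacks an LSMEANS or ESTIMATE statement, although SAP 8.1.3 promises contrasts. Nothing says a raw coefficient will be reported.

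A reader might also infer a contradiction with the Cox model. A hazard ratio for death and a rate ratio for hospitalizations are different quantities under any covariates. The Cox model shows only that the sponsor uses the simpler form elsewhere.

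Finally, a main-effects Poisson model is itself a weighted average when effects differ, with weights driven by events. True, but those weights follow the information in the enrolled sample and are not fixed at 50:50.

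**Conclusion.** The point holds as a matter of specification and efficiency. Followed as written, the plan's overall Poisson test is a 50:50 by 50:50 subgroup average, and the ANOVA becomes one if the Type III line is read.

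At 30-50% variant and 24-30% NYHA III, its variance is about 1.19-1.56 times that of a main-effects model with no prognostic effect. For Poisson it is about 1.07-1.23 with the assumed rate ratios of 1.3 and 1.5, and about 1.01 in the favourable case above. It is nil at balanced splits with equal rates. The NYHA III share and the subgroup rate ratios are assumptions; only the genotype limits come from the documents.

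Because hospitalization frequency is a component of the primary endpoint, it is tempting to read this as a flaw in the primary result, or as an invalid test. Neither is supported. The Finkelstein-Schoenfeld test (SAP 8.1.1) and the key secondary MMRM do not use these models. The interactions leave size intact, and under a common effect the estimate is unbiased. One secondary endpoint without alpha control and three exploratory endpoints are affected. It is worth correcting because the hospitalization rate ratio helps to interpret the composite, and its meaning should not depend on a software option.

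**What to change.** In SAP 8.1.4, 8.1.5 and Appendix 1.3, and in Protocol 9.3 and 9.4:

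1. Use treatment, genotype and NYHA main effects for the overall estimate and p-value, as the Cox model does.
2. Report the treatment rate ratio (Poisson) or mean difference (ANOVA) with its 95% CI through an ESTIMATE statement.
3. Test the two interactions in a separate exploratory model, alongside the subgroup analyses already planned.

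An acceptable alternative is to keep the present model and name an overall contrast weighted by the observed subgroup shares.

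The cost is a wording edit in both documents and a few lines of code, and the interaction tests move to a second model. No data collection changes.
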